Study Title: Topical bimatoprost for chemical blepharoplasty

1. Study aim, background, and design

Study aim:

Topical bimatoprost has been shown to cause periorbital changes of soft tissue which are most pronounced when used directly onto the cornea for the treatment of glaucoma. Changes are primarily felt to be the result of prostaglandin-mediated adipocyte loss, resulting in deepening of the upper eyelid sulcus and recession of infraorbital pseudoherniation. Use of topical bimatoprost to the upper eyelid margin, now FDA approved for eyelash enhancement, may provide a metered effect on the periocular tissues and allow for a topical approach to periocular rejuvenation. I propose a proof of concept, small scale study to identify change in dermatochalasis with use of bimatoprost along the lid margin.

Background:

Perception of beauty in the periocular region is influenced by several factors, including symmetry, population norms, and skin texture and tone. Soft tissue and skin changes over time create an aged appearance with the development of dermatochalasis, blepharoptosis, lacrimal gland prolapse, and fat prolapse¹. Techniques for periocular rejuvenation are well established and include soft tissue augmentation, resurfacing, and surgical correction. In May 2015, Sarnoff and Gotkin reported a case of "chemical blepharoplasty" achieved with topical bimatoprost ophthalmic 0.03% solution applied to the upper eyelid margin. After three months of use, the author noted a more youthful appearance of the periocular region, with deepening of the upper eyelid sulcus, reduction in dermatochalasis, and diminution of the inferior eyelid fat pad. These changes were attributed to the prostaglandin associated periorbitopathy (PAP), a well described phenomenon observed with the use of topical prostaglandin analogues use for glaucoma.

Periorbital changes observed with topical prostaglandin analogues are primarily due to effects on aponeurotic and deep orbital adipocytes³. Prostaglandins activate the adipocyte MAPK pathway, leading to inactivation of PPAR-gamma, inhibition of adipocyte differentiation, and decreased fat accumulation within adipocytes^{1,4}. Bimatoprost concentration-dependent contractions of ciliary muscles and activation of matrix metalloproteinases³ may also contribute to periocular changes. Patients using topical ophthalmic prostaglandin analogues commonly develop periorbital fat loss, which has been well characterized in the ophthalmology literature.

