
Bimatoprost applied to the upper eyelid margin for eyelash enhancement attempts to capitalize on the desirable effects of darker, longer, thicker eyelashes, while limiting more significant and undesirable effects through limited exposure of the drug to ocular tissues. This same concept

Version Date: 07/26/16 Version Number: 2

Page 1 of 5

may apply for dermatochalasis: at a metered dose, topical bimatoprost to the lid margin could lead to subtle periorbital fat loss resulting in improved dermatochalasis.

Study design:

This is a proof of concept study which aims to enroll a series of patients with mild to severe dermatochalasis, treat with topical bimatoprost 0.03% solution to the upper lid margin, and evaluate for cosmetic improvement of the periocular area.

15 subjects will be recruited.

2. Subject Population

Inclusion criteria: 18+, mild to severe dermatochalasis, desire for enhanced eyelashes

Exclusion Criteria: Patients with current use of ophthalmic prostaglandin analogues, history of blepharoplasty, history of neuromodulators or fillers to the periocular region or frontalis in the last 6 months, existing deep upper eyelid sulcus, opposition to eyelash enhancement, pregnancy (This small proof of concept series aims to look at a new use of an already FDA approved medication. Currently this medication is pregnancy category C and has not been studied in children. As such we will only expose the patient population in which this medication has been determined to be safe.)

Patients will be recruited through our medical dermatology and cosmetic dermatology clinics at our University by faculty and residents based on inclusion criteria.

Recruiting script:

"I am doing a study looking at the use of the medication Latisse, which is currently FDA approved for eyelash enhancement, for possible effects it could have on drooping eyelids, or dermatochalasis. Involvement in the study would involve use of the product nightly as well as monthly visits for 4 months. Would you be interested in getting more information on this study?"

3. Procedure

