At the initial visit, the study as well as known benefits and side effects of topical bimatoprost will be discussed with the patient. Written informed consent will be obtained for study inclusion, treatment, and photographic documentation. An initial examination and photodocumentation will be performed, and application instructions per the package insert. ("...should be applied every night using only the accompanying sterile applicators. They should start by ensuring their face is clean, all makeup is removed, and their contact lenses removed (if applicable). Then, carefully place one drop of LATISSE® solution on the disposable sterile applicator and brush cautiously along the skin of the upper eyelid margin at the base of the eyelashes. If any

Version Date: 07/26/16 Version Number: 2 LATISSE® solution gets into the eye proper, it will not cause harm. The eye should not be rinsed.")

Potential side effects to be discussed include potential for itching sensation of the eyes or eyelids, intraocular pressure effects, eyelid skin redness or darkening, iris darkening, unexpected hair growth or eyelash changes. Patients will be informed to contact the primary study investigator with any acute ocular changes (trauma, infection), sudden decrease in visual acuity, or eyelid/eye irritation.

The patients will be asked to use the medication nightly, and will be followed with Q 4 weeks appointments for a total of 4 visits.

Data collection:

Demographic information will be collected on all patients, including: age, sex, ethnic background.

An entry survey will be completed requesting self evaluation of the periocular area. (Appendix A)

Patients will be followed Q 4 weeks in clinic with followup photodocumentation at each visit for a total of 4 visits, 3 months of treatment.

During each visit, application instructions will be reviewed to ensure appropriate use. Each patient will be asked to complete a survey inquiring about potential side effects to ensure continued safety at followup visits (**Appendix B**), as well as an exit survey (**Appendix C**)

At completion of the study period, each patient's photographs at weeks 0, 4, 8, and 12 will be graded by 2 blinded evaluators for level of dermatochalasis: -1 (deep upper eyelid sulcus), 0 (no dermatochalasis), 1 (mild, slightly noticeable), 2 (moderate, noticeable), or 3 (severe, distinctive). Grading will be assisted by a visual aid adapted from a scale published by Shah et al. **(Appendix D)**

4. Risks

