The patients participating in the study are subject to minimal risk with use of the topical medication. If experienced, side effects such as eye or eyelid irritation, eyelid discoloration, and iris dyspigmentation will resolve with medication discontinuation. Patients may be referred to an appropriate physician specialist if needed. No direct psychological or social harm is expected.

Confidentiality of data will be maintained via a system of de-identification and password protection. First, each patient will be assigned a code (P1-15) by which they will be identified. The code key will be stored in a password protected excel document on the PI's computer. Demographic data as well as survey answers will be stored without patient names (only P#),

Version Date: 07/26/16 Version Number: 2 again in a password protected excel document.

At the cessation of the study the key will be destroyed, leaving only de-identified information.

Photographs will be taken on a digital memory card reserved only for use in the study. Photographs that include our study area, the eyes, are difficult to de-identify. Photos will include only the eyebrows and eyes in an effort to minimize face recognition. Patients will be asked to sign a separate photograph consent detailing this information.

All data is stored on a password protected laptop to which only the PI has access.

Combined, de-identified data and photographs will be used for medical education, presentations, and publication. This information is included in the consent forms.

5. Benefits

The medication is currently FDA approved for eyelash enhancement. patients can expect to see increased length and density of eyelashes.

Improvement in dermatochalasis may be seen.

6. Remuneration

There will be no payment for participation in this research study.

7. Academic or Extra Credit

NA

8. Costs

There will be no costs to the subject for participating in this research study.

9. Alternatives

The subjects do not have to participate in the research.

10. Consent process and documentation

Written informed consent will be obtained for study participation as well as medical photography.

11. Qualifications of the investigators

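### Sections 3 and 4 name eight side-effect entries and none is upper-lid hollowing, although the protocol describes it as a mechanism-based effect of the drug and grades a deep sulcus -1, past full correction

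*Protocol*

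**What the plan says.** Section 1 (Study aim) attributes the drug's periorbital changes mainly to loss of fat cells, "resulting in deepening of the upper eyelid sulcus and recession of infraorbital pseudoherniation", and says these changes are most pronounced when the drug is used on the eye itself. The Background then describes the case report behind this study, which used "topical bimatoprost ophthalmic 0.03% solution applied to the upper eyelid margin". The result is reported there as a cosmetic gain: "After three months of use, the author noted a more youthful appearance of the periocular region, with deepening of the upper eyelid sulcus". The planned regimen has the same strength and site, nightly for three months.

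The protocol also indicates how much of the effect it wants. Eyelash use is described as "limiting more significant and undesirable effects through limited exposure of the drug to ocular tissues", and by analogy "at a metered dose, topical bimatoprost to the lid margin could lead to subtle periorbital fat loss". Section 2 excludes people with an "existing deep upper eyelid sulcus". The Section 3 scale runs from 3 (severe) through 0 (no dermatochalasis) to -1 (deep sulcus).

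On risk, Section 3 promises that "known benefits and side effects of topical bimatoprost will be discussed with the patient" and then lists particular effects. Section 4 calls the risk minimal and says that "side effects such as eye or eyelid irritation, eyelid discoloration, and iris dyspigmentation will resolve with medication discontinuation". Section 5 lists possible improvement in dermatochalasis as a benefit.

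On monitoring, Section 3 provides for clinic visits every four weeks with photographs, a review of application technique and a side-effect survey (Appendix B). Two blinded evaluators grade the photographs from all four time points once the study period is over.

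**The concern.** The cosmetic effect most specific to this study's purpose appears as mechanism, entry exclusion, outcome grade and (in its wanted form) benefit, but it is not among the named risks. The drug is used here for an elective cosmetic purpose, so a patient should know that the process meant to improve the lid could also carry it past correction. Section 4's statement about resolution on stopping is not said to reach fat loss, and nothing else in the protocol addresses whether fat loss reverses.

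The second part concerns timing. Photographs that could show an early overshoot exist at weeks 4 and 8, but the only reading described comes after the last application. Gradual, painless hollowing is also outside the reasons given to patients for contacting the investigator, which are acute ocular change, sudden loss of acuity and irritation.

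**Working it through.** The protocol gives no figure of its own on this point, so the check is a comparison of texts followed by simple counts.

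**Is the effect foreseeable under this regimen?**
- Case report (Section 1): 0.03% solution, upper lid margin, three months; deepening of the sulcus reported.
- This study (Sections 1 and 3): 0.03% solution, upper lid margin, three months.
- Strength, site and duration match. The protocol's remark that fat loss is common concerns ophthalmic use and is not carried over here.

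**Does the protocol treat too much of it as an overshoot?**
- The aim is limited to subtle fat loss at a metered dose.
- On the scale, -1 lies beyond 0, which is already the absence of dermatochalasis.
- The entry exclusion is weaker evidence, since it may simply leave out people with little to treat. The undesirable effects mentioned in the Background are not specified.

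**Is it named as a risk?**
- Section 3 entries: itching; intraocular pressure effects; eyelid redness or darkening; iris darkening; hair or eyelash changes = 5.
- Section 4 entries: irritation; eyelid discoloration; iris dyspigmentation = 3.
- Total 5 + 3 = 8. Entries naming sulcus, hollowing or fat loss: 0.

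**What is read while dosing continues?**
- Photograph sets at weeks 4 and 8: 15 patients × 2 = 30. Sets with a described reading before completion: 0.
- Planned applications, taking dosing to run nightly from week 0 to week 12: 12 × 7 = 84.
- Still to come after week 4: 8 × 7 = 56, and 56/84 = 67%. After week 8: 4 × 7 = 28, and 28/84 = 33%.

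The last two lines are calendar arithmetic. They show how much dosing could still be reconsidered if a deep sulcus were visible at those visits. They say nothing about how often that happens: the protocol gives no rate of grade -1 for this route, and its only timing is one case described after three months.

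**The case against.** The strongest reply is that disclosure is already promised. Section 3 commits to discussing the study and the known side effects, and Section 1 calls the periorbital changes well described, so by the protocol's own account they are known. Both lists are open (Section 3 introduces examples, and so does Section 4), so 0 of 8 counts examples and does not measure what patients hear. The consent form and Appendix B are not shown, and either may name hollowing. All of this stands. It means the wording permits disclosure without securing it for this particular effect.

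A reader might infer that patients go uninformed or unchecked. The documents do not support that. Besides the general promise, they describe in-person visits every four weeks, a side-effect survey at follow-up, and specialist referral if needed. Continued dosing past a deep sulcus would require the investigator to miss it in clinic and the patient not to report it. What is absent is narrower: a described comparison of the photographs with baseline before the end.

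A reader might also infer that Section 4 wrongly promises that hollowing reverses. It does not say so. Its statement is attached to three other examples, and the protocol has no reversibility data either way.

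Finally, some deepening is the intended result; the case report counts it as part of a more youthful look. So a deep sulcus is not automatically a harm, and some patients may welcome it. That argues for an informed choice and against a stopping rule, which is how the remedy is framed.

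**Conclusion.** The point holds as a modest patient-safety improvement, at the level of a change that should be made. The effect is foreseeable from the protocol's own background at the planned strength, site and duration. It has its own grade beyond full correction, and none of the eight named side-effect entries in Sections 3 and 4 mentions it. No photograph comparison with week 0 is described for the 30 sets taken at weeks 4 and 8.

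The conclusion is confined to the text of those two sections. It assumes no frequency of grade -1 and no time of onset, and makes no claim about the content of the consent form or Appendix B. Confidence is medium, because those two items could narrow the gap.

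**What to change.** 1. Add upper-lid hollowing (deep sulcus) from periorbital fat loss to the Section 3 discussion list and to Section 4, and state that its reversal on stopping is not established in this protocol.
2. At the existing week 4 and week 8 visits, the investigator views that day's photograph beside week 0. If a deep sulcus has appeared, the investigator discusses with the patient whether to continue. There is no automatic stop, this reading is not shown to the evaluators, and the blinded grading at completion is unchanged.

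Cost: one phrase for the effect in each section plus the statement on reversal, and 30 comparisons of photographs already being taken. At an assumed 2 to 5 minutes each, that is 30 × 2 = 60 to 30 × 5 = 150 minutes, or 1 to 2.5 hours over the whole study, with no new visit.

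Downside: each early stopper is 1/15 = 6.7% of the sample, and the loss would be selective, because those prompted to reconsider are the strongest responders. This is containable, since the photograph showing the deep sulcus is taken before any decision to stop. Flag such patients and report their last on-drug photograph alongside week 12.
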